Period	A subdivision of the study timeline; divides stages into smaller functional segments such as screening, baseline, titration, washout, etc.
Premature patient withdrawal	Point/time when the patient exits from the study prior to the planned completion of all study treatment administration and/or assessments; at this time all study treatment administration is discontinued and no further assessments are planned, unless the patient will be followed for progression and/or survival
Stop study participation	Point/time at which the patient came in for a final evaluation visit or when study treatment was discontinued whichever is later
Study treatment	Includes any drug or combination of drugs in any study arm administered to the patient (subject) as part of the required study procedures, including placebo and active drug run-ins. In specific examples, it is important to judge investigational treatment component relationship relative to a study treatment combination; study treatment in this case refers to the investigational and non-investigational treatments in combination.
Study treatment discontinuation	Point/time when patient permanently stops taking study treatment for any reason; may or may not also be the point/time of premature patient withdrawal
Supportive treatment	Refers to any treatment required by the exposure to a study treatment, e.g. premedication of vitamin supplementation and corticosteroid for pemetrexed disodium.
Variable	Identifier used in the data analysis; derived directly or indirectly from data collected using specified assessments at specified time points

1. Background

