Patients whose treatment is interrupted or permanently discontinued due to an AE including abnormal laboratory value must be followed at least once a week for 4 weeks and subsequently at 4-week intervals until resolution or stabilization of the event, whichever comes first. Dose interruptions should be reported on the appropriate Dosage Administration case report form (CRF). The maximum time allowed for toxicity-related treatment interruption is 21 days (3 weeks) from the intended dosing day. If interruption is > 3 weeks, the patient must be discontinued from the study treatment. However, the patient will continue to be followed for toxicity.

7. Population

Metastatic NSCLC: Male or female patients aged ≥ 18 years with histologically or cytologically confirmed metastatic squamous or non-squamous NSCLC whose disease has progressed after a platinum-based chemotherapy and after a single-agent immunotherapy. Patients with *EGFR* or *ALK* genomic tumor aberrations should have disease progression on FDA-approved therapy for these aberrations prior to receiving nivolumab. The investigator or designee must ensure that the patient meets all the inclusion and none of the exclusion criteria before being offered enrollment in the study.

Metastatic Uveal Melanoma: Male or female patients aged ≥ 18 years with histologically or cytologically confirmed metastatic uveal melanoma that is immunotherapy naïve.

Study Duration:

After administration of ADV/HSV-tk + Valacyclovir followed by SBRT, nivolumab will be given every 4 weeks from day 17 until disease progression, unacceptable toxicity, or up to 12 months in patients without disease progression. Patients will be followed up for 6 months or until disease progression, whichever occurs first. Patients will be assessed for AEs up to and including 30 days after the last treatment dose.

Safety Criteria:

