A screening medical history and physical exam will be performed (baseline symptom-medical history and physical examination are not required if the screening was conducted within 7 to 28 days prior to day 0 of ADV/HSV-tk). Patients presenting with any medical history, physical exam, or laboratory abnormality that, in the opinion of the treating physician, would put their safety at risk will be excluded. A window of ± 5 days is allowed for study visits and assessments (except as otherwise specified). A physical exam will be performed on days 0 and 17; every 4 weeks thereafter until completion of the protocol-specified treatment; and at end of treatment (EOT). Vital sign (blood pressure, heart rate, and oral temperature) measurements will be performed at each physical exam. A 12-lead electrocardiogram (ECG) will be performed at screening, at EOT, and when clinically indicated. Multigated acquisition (MUGA) scan or echocardiogram (ECHO) will be performed when clinically indicated. The same method (ECHO or MUGA scan) must be used throughout the duration of the study. A blood sample for complete blood count (CBC) with platelet count and differential white blood cell (WBC) count will be obtained at screening, on days 0 and 17, every 4 weeks thereafter until completion of the protocol-specified treatment, at EOT, and when clinically indicated. If a patient is found to have an absolute neutrophil count (ANC) $< 1.5 \times 10^9/L$, platelet count $< 100 \times 10^9/L$, or both, the CBC with differential should be repeated at least every other day until the ANC and platelet count have exceeded these values. A blood sample for clinical chemistry panel (glucose, albumin, sodium, potassium, carbon dioxide, chloride, blood urea nitrogen [BUN], creatinine, total bilirubin, alkaline phosphatase, aspartate transaminase [AST], and ALT) and evaluation of magnesium and lactate dehydrogenase will be obtained at screening, on days 0 and 17, every 4 weeks thereafter until completion of the protocol-specified treatment, at EOT, and when clinically indicated. Prothrombin time (PT), international normalized ratio (INR), and activated partial thromboplastin time (aPTT) testing will be performed at screening, on day 17, every 4 weeks thereafter until completion of the protocol-specified treatment, and at EOT. For women of childbearing potential (WOCBP), the results of a serum β -human chorionic gonadotropin (β -hCG) pregnancy test must be negative within 7 days of the administration of the first treatment dose. If the screening serum β -hCG pregnancy test is performed more than 7 days before ADV/HSV-tk dosing, it must be repeated at baseline, with results known to be negative prior to the administration of the first dose of the study treatment. Serum β -hCG pregnancy testing is to be repeated as clinically indicated. Laboratory tests may be done more frequently if medically indicated. Patients will be assessed for AEs and SAEs from informed consent signing up to and including 30 days after the last treatment dose. Study treatment-related AEs occurring beyond 30 days after the last dose of nivolumab and any study patient death should also be reported. Toxicity will be defined as any treatment-related death or any \geq Grade 3 toxicity excluding alopecia and constitutional symptoms as assessed by NCI CTCAE v4.03. Patients whose treatment is interrupted or permanently discontinued due to an AE including

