Investigations	Alkaline phosphatase increase (14-22%), ALT increase (12-16%), AST increase (16-28%), Total bilirubin increase (3-19%), Creatinine increase (13-22%), Weight decrease (13%, severe 1%).
Metabolism and nutrition	Decreased appetite (35%, severe 3%).
Musculoskeletal and connective tissue	Arthralgia (13%), Musculoskeletal pain (36%, severe 6%).
Respiratory, thoracic, and mediastinal	Cough (17%).
Skin and subcutaneous tissue	Pruritus (19%), Rash (21%, severe <1%).

Clinically significant immune-mediated adverse reactions can occur, including pneumonitis, colitis, hepatitis, nephritis, hypothyroidism, and hyperthyroidism. Immune reactions may be delayed or occur after nivolumab discontinuation. Based on the type and severity of the reaction, management may include withholding or discontinuing nivolumab, administering HD corticosteroids, and if appropriate, initiating hormone replacement therapy. Following resolution of the reaction to grade 1 or less, corticosteroids should be tapered over at least one month. Nivolumab should not be resumed while the patient is receiving immunosuppressive doses of corticosteroids or other immunosuppressive therapy. Restarting nivolumab may be considered following completion of corticosteroid taper. Permanent discontinuation of nivolumab is usually recommended following grade 3 or 4 immune-mediated reactions.

Supply and storage:

Injection: Bristol-Myers Squibb Company supplies nivolumab as 40 mg and 100 mg ready-to-use, single-use (preservative-free) vials in a concentration of 10 mg/mL. Refrigerate and store in original packaging to protect from light. Do not freeze or shake.¹⁸⁹

Solution and compatibility:

- Nivolumab should be clear and colorless to pale-yellow in color. Discard if cloudy or discolored.
- Nivolumab can be infused undiluted (10 mg/mL) or diluted with normal saline or 5% dextrose in water (to 0.35 mg/mL or greater).

Parenteral administration:

Intermittent infusion over 60 minutes.

Dosage guidelines:

The ENSIGN protocol's guidelines for dosing also include consideration of ANC. Dosage may be reduced, delayed, or discontinued in patients with bone marrow depression due to cytotoxic therapy/RT or other toxicities. (See Section 6 for management of immune-mediated complications of nivolumab)

Table 7. Nivolumab adult dosing

Route	Cycle Length:	Dose
IV	4 weeks	480 mg IV for one dose on day 1 (Total dose per cycle, 480 mg)

Table 7

10. Prohibited concomitant therapy

Antineoplastic therapies

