^jRelapsed/refractory and/or metastatic patients will be evaluated with /CT scan of the thorax, abdomen, and pelvis at screening, every eight (8) weeks thereafter until completion of the protocol-specified treatment and/or at the discretion of the treating physician, at EOT, and when clinically indicated. For patients with equivocal CT scan results, PET scan will be performed.

^kIn patients with accessible tumor, biopsies will be conducted at Visit 1, after the first dose of nivolumab (\pm 2 days), and if the patient progresses while on treatment, before the patient starts the new treatment.

Banked tumor tissue obtained as part of the patient's standard care and additional biopsies will be evaluated at a later time for assessment of Th1 response (IL-1, IL-2, IL-6, IL-12, IFN- α , and GM-CSF) and TILs before and after ADV/HSV-tk + Valacyclovir therapy.

^lBlood samples for correlative studies will be collected at screening, after the first dose of nivolumab (\pm 2 days), and at the end of Cycle 2 of nivolumab. An additional sample will be collected from patients whose disease progresses while on treatment. Blood samples will be collected into standard vacutainer tubes (3 green top tubes). Samples will be evaluated for profile of circulating suppressor and effector immunocytes and cytokines.

^mADV/HSV-tk will be injected intratumorally at 5×10^{11} viral particles in a 2-mL total volume on day 0 of the study. The study coordinator will dispense the 14-day quantity of Valacyclovir on Day 0 of the study. The patient will be instructed to take Valacyclovir (2 g) orally t.i.d. for 14 days (day 1 to day 15 of the study). NOTE: For patients with serum creatinine level between 1.6–2.0 \times ULN, valacyclovir dose will be reduced 50% (i.e., 1 g t.i.d.).

SBRT of 30 Gy (6 Gy X 5 fractions) will be administered over 2 weeks from day 2 to day 14 of the study. Nivolumab (480 mg) will be administered intravenously over 30 minutes every 4 weeks (\pm 1 day) starting on day 17 (\pm 1 day) of the study and continuing until disease progression, unacceptable toxicity, or up to 12 months in patients without disease progression.

ⁿAEs and SAEs will be captured from the time of informed consent signing up to and including 30 days after the final dose of nivolumab. Study treatment-related SAEs occurring beyond 30 days after the last dose of nivolumab and any study patient death should also be reported.

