12.5 Pregnancy

WOCBP must have a negative serum pregnancy test within 7 days of the administration of the first study treatment. Pregnancy testing is required at screening or whenever pregnancy is suspected.

WOCBP, defined as all women physiologically capable of becoming pregnant, must use highly effective contraception during the study and for 5 months after stopping nivolumab. Highly effective contraception is defined as either:

- Total abstinence: When this is in line with the preferred and usual lifestyle of the subject (periodic abstinence [e.g., calendar, ovulation, symptothermal, post-ovulation methods] and withdrawal are not acceptable methods of contraception)
- Sterilization: Surgical bilateral oophorectomy (with or without hysterectomy) or tubal ligation at least six weeks before study treatment start. In the case of oophorectomy alone, only when the reproductive status of the woman has been confirmed by follow-up hormone level assessment.
- Male partner sterilization (with the appropriate post-vasectomy documentation of the absence of sperm in the ejaculate). (For female subjects on the study, the vasectomized male partner should be the sole partner for that subject)
- Use of a combination of both of the following:
 - Placement of an intrauterine device (IUD) or intrauterine system (IUS)
 - Barrier methods of contraception: Condom or occlusive cap (diaphragm or cervical/vault caps) with spermicidal foam/gel/film/cream/vaginal suppository

Sexually active males must use a condom during intercourse while enrolled in the study and for 5 months after stopping treatment and should not father a child in this period. A condom is required to be used also by vasectomized men to prevent delivery of the drug via seminal fluid. Female partners of male patients must also be advised to use one of the following contraception methods: (1) IUD or IUS or (2) prior male/female sterilization.

13. Safety monitoring and reporting

Information about all AEs, whether volunteered by the subject, discovered by investigator questioning, or detected through physical examination, laboratory test, or other means, will be collected, recorded, and followed as appropriate.

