14.3 Pregnancy

To ensure patient safety, each pregnancy occurring while the patient is on study treatment must be reported to the local IRB within 24 hours of learning of its occurrence. The pregnancy should be followed up to determine outcome, including spontaneous or voluntary termination, details of the birth, and the presence or absence of

any birth defects, congenital abnormalities, or maternal and/or newborn complications. The newborn will be followed for at least 12 months.

Pregnancy should be recorded on a Clinical Trial Pregnancy Form and reported by the investigator to the local IRB. Pregnancy follow-up should be recorded on the same form and should include an assessment of the possible relationship to the study treatment and any pregnancy outcome. Any SAE experienced during pregnancy must be reported on the SAE Report Form.

15 Statistical methods

15.1 Sample size.

Study Design and Sample Size Calculation: For the NSCLC cohort, a sample size of 16 patients achieves 80.3% power to detect the difference between a null hypothesis of ORR of 3% and treatment ORR of 25% (alternative hypothesis) at a 0.05 significance level (i.e., alpha) in a one-sided Fisher's exact test. For the uveal melanoma cohort, a sample size of 9 patients achieves 80.4% power to detect the difference between a null hypothesis of ORR of 3% and treatment ORR of 30% (alternative hypothesis) at a 0.05 significance level (i.e., alpha) using a one-sided Fisher's exact test. Power calculations were performed using nQuery Advisor 7.0. For both the NSCLC and uveal melanoma cohorts, an initial cohort of 3 patients will be followed for toxicity through the first cycle of nivolumab. If only 1 of 3 patients experience toxicity, then 3 more patients will be enrolled. If no more than 1 of 6 patients experience toxicity, then the trial will be fully opened. The staggering interval will be 5 weeks for the run-in cohort. Toxicity will be defined as any Grade 3 or greater toxicity excluding alopecia and constitutional symptoms as assessed by NCI CTCAE v4.03. Hematological toxicities will have a window of 21 days to resolve.

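### Pregnancy reporting stops with treatment although contraception is required for 5 more months, and the sections disagree on which adverse events are reportable after day 30

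*Combined protocol and SAP*

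**What the plan says.** **Pregnancy.** Section 14.3 sets the trigger: "each pregnancy occurring while the patient is on study treatment must be reported to the local IRB within 24 hours". Outcome follow-up and at least 12 months of newborn follow-up are described for pregnancies reported in this way. The glossary defines study treatment discontinuation as "Point/time when patient permanently stops taking study treatment for any reason". Section 12.5 sets a longer precaution period. Women of childbearing potential "must use highly effective contraception during the study and for 5 months after stopping nivolumab". For men, "Sexually active males must use a condom during intercourse while enrolled in the study and for 5 months after stopping treatment". Section 9.4 repeats the 5 months for women and gives possible fetal harm as the reason.

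**Adverse events.** Section 7 (Study Duration) states: "Patients will be assessed for AEs up to and including 30 days after the last treatment dose". What follows that window is worded in two ways:

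- Section 7 (Safety Criteria): "Study treatment-related AEs occurring beyond 30 days after the last dose of nivolumab and any study patient death should also be reported". Section 12 has the same rule in nearly the same words.
- Section 11, visit-schedule footnote: "Study treatment-related SAEs occurring beyond 30 days after the last dose of nivolumab and any study patient death should also be reported".

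Section 9.4 warns that "Immune reactions may be delayed or occur after nivolumab discontinuation", without saying for how long.

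**The concern.** A pregnancy that begins in the 5 months after stopping falls inside the period in which the protocol tells patients to avoid conception. Yet section 14.3 does not require it to be reported, followed to outcome, or followed through the newborn period. Few such pregnancies are likely in this population, but the information lost in each case would matter.

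The AE discrepancy bears on a named secondary endpoint. Section 4 defines toxicity as treatment-related death or any event of Grade 3 or higher, with exclusions for alopecia and constitutional symptoms. Section 15.1 reports the worst grade per patient. If staff working from the footnote record only serious late events, and staff working from section 7 or 12 record all related ones, the toxicity numerator depends on which page was open.

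**Working it through.** The plan states no figure for this point, so the check compares time windows and wording.

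**1. Pregnancy window.** Inputs: contraception for 5 months after stopping (section 12.5); reporting during study treatment (section 14.3); 4-week nivolumab cycles (sections 6 and 9.4).

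- Length of the period: 5 × 365.25 / 12 = 152.2 days.
- If treatment ends at the last dose, reporting covers 0 of these days and about 152 are uncovered.
- If treatment is assumed to run to the end of the last 28-day cycle, 152.2 − 28 = 124.2 days are uncovered.

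The gap is therefore about 124 to 152 days. The glossary definition points to the longer figure.

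**2. Post-30-day rule.** Take a related, non-serious Grade 3 event first seen 40 days after the last nivolumab dose.

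| Source | Reportable? |
|---|---|
| Section 7, Safety Criteria | Yes (related AE) |
| Section 12 | Yes (related AE) |
| Section 11 footnote | No (related SAEs and deaths only) |
| Section 4 toxicity definition | Counts (Grade 3 or higher; no time limit stated) |

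Such an event can exist: section 13.1.2 says that Grade 3 or 4 does not by itself make an event serious.

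**3. Effect on the toxicity rate.** Inputs: 16 NSCLC and 9 uveal melanoma patients (section 15.1). The number of affected patients is not known, so a range is shown. It assumes full cohorts as denominators and no earlier qualifying event in the affected patients.

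| Patients affected | NSCLC, k/16 | Uveal melanoma, k/9 |
|---|---|---|
| 0 | 0 | 0 |
| 1 | 6.3 points | 11.1 points |
| 2 | 12.5 points | 22.2 points |

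**4. The clock.** The 30 days run from the last dose of study treatment in section 7 (both subsections) and section 13.1.1. They run from the last nivolumab dose in section 12 and the section 11 footnote. The AE row of the section 11 table counts from the last dose of treatment, while its own footnote counts from nivolumab. The two agree for any patient whose last treatment is nivolumab. They differ for a patient who stops before day 17 and never receives it.

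**The case against.** **Safety collection does not end at day 30.** A reader might infer that it does. The documents do not support that: deaths and related events (AEs in sections 7 and 12, SAEs in the footnote) stay reportable with no end date. Section 14.2 also asks for related or unexpected events within 24 hours of awareness, and section 17 extends the duty to information learned after participation ends. This stands, so the point concerns which late events are reportable, not whether any are.

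**No protocol-set immune-AE window is cut short.** It is tempting to divide 30 days by the 152-day contraception period and say that active AE assessment covers only 20% of the risk period. Section 9.4 gives no duration for delayed immune reactions, so that ratio borrows a window set for another purpose. Nor can a typical end of collection be dated from median PFS in the cited studies. Those were other treatments and populations, and section 12.3 allows treatment to continue after confirmed irPD.

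**Patients stopped before day 17 are not left without an end date.** Sections 13.1.1 and 14.2 count 30 days from the end of study treatment, which covers them. Only the inconsistency of wording remains.

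**Part of the pregnancy gap is covered.** A congenital anomaly is an SAE under section 14.1, and section 17 names the birth of an affected child as late reportable information. That does not prompt a report of a miscarriage, a termination or a normal birth. On partners, section 14.3 speaks of each pregnancy during the patient's treatment, which could include a partner's. It is therefore too strong to say that partner pregnancies are always excluded; the text is ambiguous.

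**Conclusion.** Two defects hold on the text. First, the reporting trigger in section 14.3 is shorter than the protocol's own contraception period by about 152 days (about 124 if treatment is taken to run to the end of the last cycle), and the status of partner pregnancies is unclear. Second, sections 7 and 12 contradict the section 11 footnote on what is reportable after day 30. One patient can shift a cohort's toxicity rate by 6.3 or 11.1 percentage points, under the assumptions stated above. The differing clock wording is a lesser inconsistency of the same kind.

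Both affect the completeness and consistency of safety data. Neither affects the ORR analysis. How many events would be involved cannot be estimated from the documents and may be none. The case for change is that the passages must be reconciled and that doing so costs little.

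**What to change.** - **Section 14.3:** require reporting and outcome follow-up for any pregnancy in a patient or a male patient's partner, from the first study dose to the end of the 5-month period already in section 12.5. If nivolumab was never given, count from the last dose of any study treatment.
- **Sections 7, 11 (footnote) and 12:** use one post-30-day rule that captures related AEs, at least those of Grade 3 or higher, so that it matches the toxicity definition in section 4.
- **Clock:** use 30 days after the last dose of any study treatment throughout, as in section 13.1.1, and anchor the post-30-day rule to the same date.
- **Optional:** ask about late immune-mediated events at the follow-up contacts already planned. The protocol sets no 5-month AE window, so a fixed schedule of extra calls to that point would be a design preference and is not needed to resolve this point.

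The cost is a wording amendment and matching CRF and pregnancy-form instructions, for a planned 16 + 9 = 25 patients. No extra visits are required. Following a partner's pregnancy would need the partner's agreement. The contraception requirements and treatment rules do not change.
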